Randomization will be stratified by sex (male/female) and laterality (unilateral/bilateral) within each clinical site. Within each stratum, patients will be allocated in a 1:1 ratio to either 2-year or 4-year bracing using a variable block size to ensure that there is no temporal bias and that the two study arms will be balanced by gender and laterality within each site. Randomization sequences will be generated with SAS software (SAS Institute Inc., Cary, NC, USA) by the study statistician *a priori*. When a participant is ready to be randomized, the site coordinator will access a secure and password-protected website, provide the participant's study ID number, identify the appropriate stratum, and verify that the participant fulfills the eligibility requirements. The website will then access the randomization sequence for that stratum, determine the next treatment assignment, and elicit the treatment assignment. A study subject will be randomized and assigned to treatment only when it has been determined that he/she has satisfied all the eligibility requirements for the study and informed consent for the intervention phase has been obtained.

To ensure that we are collecting quality data, we developed valid and logically consistent case report forms that will be used in these studies. Clinical information includes severity (Pirani score), age at treatment initiation, sex, laterality, family history of clubfoot in first degree relative, number of casts required to treat, use of tenotomy, and the presence of the drop toe sign (Edmonds and Frick 2009). Individuals collecting and entering data will be adequately trained, and data will be monitored to ensure that the database is accurate.

The coordinator will download the data from the dose monitor at each 3-month visit, and re-launch it so it can be remounted by the orthotist. The data will be saved as a comma delimited file and the file will be uploaded into the data entry system by the site coordinator..

3. Casting and Bracing Protocol

The Ponseti method of casting will be followed and all PI's are Ponseti certified physicians. Tenotomy will be performed before last cast application for any foot that cannot achieve at least 10° of ankle dorsiflexion as measured with a hand-held goniometer. The foot will be considered corrected if greater than 50° of foot abduction and greater than 10° of ankle dorsiflexion can be achieved, both measured with hand-held goniometer. Those feet that

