are not fully corrected will undergo further casting until correction is achieved before starting the bracing protocol. The number of casts required to achieve correction will be recorded as well as any casting complications. After achieving correction all patients are fitted **with a foot abduction brace (FAB) consisting of shoes attached to a bar**. The type of FAB used will be based on physician and family preference but the common factor between all braces will be the presence of a bar connecting the shoes. The presence of a bar has been shown to be the crucial feature of clubfoot bracing (Janicki 2011). All caregivers will be instructed to place child in the FAB 23 hours a day for three months and then night time use (eight to twelve hours) hours a day for 2 versus 4 years based on treatment arm. All braces will include an implanted temperature logger that will be launched by the research coordinator prior to mounting.

All centers will provide the names and credentials of the orthotists they plan to work with for the study. The orthotist will adjust pads, areas of relief, and straps as needed to optimize fit. Clubfoot recurrence will be determined by the treating physician and treated with repeat casting followed by FAB use. Recurrence is defined as the development of any of the following deformities in isolation or in combination that require repeat cast application or surgical intervention: hindfoot varus, hindfoot equinus, forefoot adduction, forefoot cavus, or forefoot.

The Coordinating Center will develop manuals of operations to standardize patient management. However, variability in practices is allowed and will be at the discretion of the physician and orthotist at each clinical site. This may impart some variation in care across the centers, but will realistically mimic the current state of the art for the best care possible. Randomization within sites will minimize the potential bias introduced by differences in patient populations and management across sites and orthotists

4. Follow-Up Schedule

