Study subjects will be seen every 3 months. Interim visits for brace fitting and consultation or family discussions with the physician/coordinator/orthotist will be allowed and encouraged. Local coordinators will contact the patient and family via phone at least monthly to provide the opportunity for questions, discussion, and feedback as needed. Subjects will be evaluated at each visit of the current state of their clubfoot and will be told if there are any signs of recurrence. Parents have the right to withdraw from the study at anytime.

5. Study Endpoint

Although follow-up data will be collected for the duration of the trial, the data collected at 1-year follow-up post completion of treatment arms will be used for the primary analysis to address the question asked in specific aim 1a. This ensures that patients in both treatment arms are followed for the same amount of time after they finish bracing.

6. Statistical Analysis

General

The goal of this study is to establish the time-dependent risk for recurrence within the first year post-treatment and evaluate factors associated with recurrence in isolated clubfoot. Kaplan-Meier survival curves that describe the time to recurrence will be generated, with

95% confidence bounds placed around the probabilities that this event will occur at pre-defined intervals. Of particular interest will be an assessment of the hazard ratio, with 95% confidence bounds, that compares recurrence in patients receiving 2-year versus 4-year bracing. While the goal of this study is to detect an overall treatment difference, Cox regression analysis will determine whether covariates that include compliance with bracing, gender, laterality, age, Pirani score, and family history are associated with the probability that relapse will occur. A separate Cox model will be used for each covariate.

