Additional analyses include mixed model repeated measures analysis of variance to determine if the magnitude of changes in exam findings differs according to whether a recurrence ultimately occurs. Unlike traditional repeated measures analyses, the mixed model method allows for the inclusion of patients with incomplete data. The focus of these analyses will be the interaction between recurrence group and time point; interactions that test hypotheses regarding the equality of changes over time in the two groups. Within the mixed model, appropriate statistical contrasts will be used to test the null hypothesis that changes between two specific time points in one group are equal to corresponding changes in another group.

Simple t-tests and chi-square tests will be used to determine if characteristics at study enrollment differ according to whether there is recurrence. Receiver operating characteristic (ROC) curve analysis will be performed to determine if measures of compliance discriminate patients that recurrence from patients that do not recurrence.

These data will be analyzed with an "intention to treat" principle; wherein patients will be included in the intervention group as determined by the randomization, independent of compliance. Secondary analyses will be performed to evaluate the effects of treatment independent of crossover by examining outcomes relative to actual treatment status.

For all analyses, careful attention will be given to whether the data satisfy the distributional and model-specific assumptions of the procedures used. Appropriate data transformations or non-parametric methods will be used as appropriate.

It is important to point out that this study is not designed to (1) assess the safety or efficacy of a particular brace; (2) compare outcomes across clinical sites. All sites will use foot abduction braces. To avoid any perception of conflict of interest and to follow recommendations from the Disclosure Review Committee, the type of particular brace used will not be recorded in the study data. Brace type is inherently associated with clinical site and site physician. As such, the following variables will not be included as effects of interest in the analytic models: brace type, clinical site, physician, and orthotist.

Heat sensor data (analysis)

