If, after the first review, it is determined the power of the study will be compromised due to low enrollment, and if low enrollment is due to patients' desire NOT to randomize, we will consider adding a restricted cohort parallel trial in which eligible patients who decline randomization will be asked to enroll in an observational arm where they are free to choose between the two treatment arms. All facets of the protocol will be implemented except randomization. This restricted cohort design has been recommended by several authors, and a variation of it is being used in the SPORT study headed by James Weinstein. A separate set of analyses would be conducted for the observational cohort, again using intention-to-treat, and as-treated analyses. Because the treatment groups will not be balanced by randomization, we would use propensity score analysis to control for the propensity to choose one treatment over another. The propensity score enters the regression equation, allowing for a straightforward evaluation of the estimated treatment versus control effects that reflect adjustment of differences in observed background characteristics. This method has been widely used in health services and clinical research as an alternative to randomized designs (Brener et al. 2004).

2. Crossovers, Dropouts, and Subjects Lost to Follow-Up

Subjects/parents requesting crossover or to exit the study will have their questions and concerns addressed. Both options will be allowed in deference to the subject's right to self-determination. However, neither option will be suggested or encouraged by any member of the team. All participants, regardless of crossover to an alternate treatment or study dropout will follow all other study procedures to the study end, unless a participant refuses to continue in the study by withdrawing his/her consent. In the intention-to-treat analysis, subjects will be analyzed in the treatment to which they were randomized.

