An "as-treated" analysis will be performed in addition to the primary intention-to-treat analysis to take into account the effect of crossover and dropout. It should be remembered that crossover occurs in the typical clinical setting whenever the patient either doesn't wear the brace at all, wears the brace at a less-than-effective dose, or when the patient or physician requests a brace after a period of observation. If a subject crosses over from observation to bracing treatment, we will be able to account for the patient's characteristics at the time of cross-over, and the dose monitor will allow measurement of subsequent time in brace. A 10 percent lost-to-follow-up rate has been taken into account in the sample size/power calculations. Although unrealistic, only a 0% rate of loss to follow-up guarantees the benefits of randomization. We will employ several proven strategies to minimize loss to follow-up, including education concerning the full burden of trial participation, minimization of respondent burden in terms of visits and questionnaires, obtaining at least one alternative contact for each subject, as well as phone calls and other reminders of upcoming visits. The seven centers have a documented ability to cover a 15% rate of dropout that is 5% greater than the estimate used for planning purposes. If dropouts exceed this during the recruitment phase, then centers from the alternate list will be brought into the study. If excessive dropouts occur during the follow-up phase of the study, no additional centers will be recruited and instead, attempts to locate the patient and determine final outcome will be made, and if needed, statistical methods will be employed to compensate for missing data.

Summary of Research Proposal

Clubfoot is a common and severe musculoskeletal birth defect. Although clubfoot is often successfully treated with the Ponseti method, some clubfeet relapse in the following years. One goal of this study is to provide clinically useful information regarding the optimal length of abduction bracing that is necessary to prevent clubfoot recurrence. A second goal of this study is to investigate the other variables (clinical, bracing compliance) that influence clubfoot recurrences. These studies have great potential to impact the care and treatment of patients with clubfoot.

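### Does the observation-to-bracing crossover wording, with no written rule for treatment actually received, undermine the secondary as-treated analysis?

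*Combined protocol and SAP*

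**What the plan says.** Under Randomization and Data Collection, "patients will be allocated in a 1:1 ratio to either 2-year or 4-year bracing". Under Casting and Bracing Protocol, every corrected foot goes into a brace, and a recurrence is "treated with repeat casting followed by FAB use".

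The General part of Statistical Analysis makes intention-to-treat the governing principle and adds secondary analyses to "evaluate the effects of treatment independent of crossover by examining outcomes relative to actual treatment status". The section on crossovers, dropouts and loss to follow-up repeats that an as-treated analysis will supplement the primary one. On crossover it says three things:

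- Participants, "regardless of crossover to an alternate treatment or study dropout will follow all other study procedures to the study end", unless consent is withdrawn.
- In ordinary practice, crossover happens when a patient does not wear the brace, "wears the brace at a less-than-effective dose, or when the patient or physician requests a brace after a period of observation".
- For this trial in particular, it adds: "If a subject crosses over from observation to bracing treatment", the study can account for the child's "characteristics at the time of cross-over, and the dose monitor will allow measurement of subsequent time in brace".

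Study Endpoint says that "the data collected at 1-year follow-up post completion of treatment arms will be used for the primary analysis". It does not say which clock the as-treated analysis uses.

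**The concern.** Two things look wrong. First, no child is randomised to observation, so a move from observation to bracing is not a move between the arms. The wording reads as if carried over from a brace-versus-no-brace design.

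Second, no rule assigns a child to 2-year or 4-year treatment as received. The plan does not say when status is fixed, where the clock starts, or whether bracing after a recurrence counts. The 80% wear threshold in the heat-sensor section is an example for comparing recurrent with non-recurrent children, so it does not fill the gap.

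The gap would matter because a child must stay recurrence-free to complete an uninterrupted 4-year course, and a child who recurs is braced again. If children were regrouped by time braced, the grouping would depend partly on the outcome. The as-treated result could then point either way with no true effect, and the rule could be chosen after the data were seen.

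**Working it through.** **The plan's own figures.** The plan gives no figure for the as-treated analysis. Its power table, with 55 completers per group and two-sided alpha 0.05, reproduces with the pooled normal approximation: 0.990, 0.963 and 0.787 against the stated 0.99, 0.96 and 0.80. None of these depends on how crossover is defined.

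**Assumptions for the check (not in the documents).** There is no true effect of duration. The relapse rate is constant at p = 5%, 10% or 15% a year, so the hazard is h = −ln(1 − p). In the 4-year arm 10% or 20% stop early, uniformly over years 0 to 4. In the 2-year arm 0, 10% or 20% continue, stopping uniformly over years 2 to 4. Follow-up is 5 years from brace start. This gives 3 × 2 × 3 = 18 combinations.

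**Long-versus-short rate ratios with no true effect.** The first figure is at 10% a year with 20% departures in each arm; the range covers all 18 combinations.

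| Rule for treatment received | Ratio | Range |
|---|---|---|
| As randomised | 1.00 | 0.99–1.01 |
| Landmark at 2 years among recurrence-free children | 1.00 | 0.99–1.01 |
| Switch counted only if made while recurrence-free | 0.99 | 0.91–1.18 |
| Braced more than 2 years, counted up to recurrence | 0.38 | 0.36–0.44 |
| As above, plus 0.25 year of re-bracing | 0.82 | 0.62–1.48 |
| As above, plus 1 year of re-bracing | 1.57 | 1.11–3.04 |

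**Where the 0.38 comes from.** Remove all crossover and apply the up-to-recurrence rule at 10% a year. Then h = −ln 0.9 = 0.10536. The share relapse-free is 0.9² = 0.81 at 2 years and 0.9⁵ = 0.59049 at 5 years. Per one child in each arm:

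- Long group (4-year arm, relapse-free past year 2): events 0.81 − 0.59049 = 0.2195; child-years 2 × 0.81 + 0.2195/0.10536 = 3.703; rate 0.0593.
- Short group (all of the 2-year arm, plus 4-year children relapsing by year 2): events 0.4095 + 0.19 = 0.5995; child-years 0.4095/0.10536 + (0.19/0.10536 − 2 × 0.81) = 3.887 + 0.183 = 4.070; rate 0.1473.
- Ratio 0.0593/0.1473 = 0.40.

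So nearly all of the distortion is present when nobody crosses over. It comes from moving 4-year children who relapsed early into the short group, although they never left their assigned regimen. With no crossovers, a rule based on crossover returns the randomised comparison, 1.00.

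**The text on what defines status.** The statistical section asks for effects independent of crossover, and the crossover section speaks of an alternate treatment. With two arms, the alternate to 2 years is 4 years and the reverse. Not wearing the brace can cover a 4-year child who stops; asking for a brace after a period without one can cover a 2-year child past the scheduled stop. Re-bracing is treatment for the event, so in a time-to-recurrence analysis it comes too late to define exposure.

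**Whether a more elaborate model would help.** The obvious alternative is a Cox model with current brace status as a time-dependent covariate. At 10% a year with 55 per arm, about 17 recurrences fall in years 2 to 4. With information 4.65, the 95% interval spans a factor of exp(1.96/√4.65) = 2.5 either side. It is also unbiased only if stopping the brace is unrelated to impending relapse. Suppose 10% of relapsing children stop three months before the relapse is recorded, with no true effect: current brace status then gives about 0.58.

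**The case for a change.** The best case for a change is that crossover is expressly allowed, so the as-treated analysis will be used and read beside the intention-to-treat result. The text gives no rule, the observation wording is about this study and not only general practice, and a definition would cost a few sentences. An unwritten rule leaves room for choice after the data are seen, and the table shows how far apart the choices can lie.

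Much of this is right. The wording does not fit the design and the definition is not written down. The crossover-based reading is not exactly null either: it reaches 1.18 when 20% of the 4-year arm stop early and no 2-year child continues, and its false-positive rate is 5% to 10% against a nominal 5%.

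What does not stand is the size. The extreme ratios need rules that the plan never states and that sit badly with its tie to crossover. A written rule would also not make the analysis confirmatory. Families are told of signs of recurrence at each visit, so stopping or continuing may follow early signs whichever definition is chosen. The time-dependent model answers a different question, on-brace against off-brace, imprecisely and with the same exposure to early signs. Censoring children at dropout would sit badly with the plan to keep following them and to seek a final outcome.

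**Conclusion.** No change is needed. The observation phrase is a slip in wording, and the missing rule is a detail of a secondary analysis that analysts can supply from the text: a child has crossed over if he or she departed from the assigned duration before any recurrence. The heat-sensor downloads, 3-month visits and continued follow-up provide the data to date such departures. On that reading the null rate ratio is 0.99, with a range of 0.91 to 1.18. The figures of 0.38 and 1.57 arise only under regrouping by time braced, which the plan does not call for.

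The sizes rest on assumed relapse and departure rates, a constant hazard, and departures unrelated to relapse. The firmer part is structural: without crossovers, a crossover-based definition reproduces the randomised comparison and a time-braced definition does not. Grouping for the primary intention-to-treat analysis is untouched. If relapse risk falls with age, a clock that starts when bracing stops compares children of different ages: with assumed rates of 10% and 5% a year, ln(0.95)/ln(0.90) = 0.49. That belongs to the choice of endpoint clock, is present with no crossover at all, and is a separate matter from this one.
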